## 1.4. Safety in humans

As of 19 January 2021, 310 subjects, including 102 healthy male subjects of sub-Saharan African origin in DNDiOXA001, 208 patients with HAT in DNDi-OXA-02-HAT study and 6 healthy Caucasian male subjects in DNDi-OXA-03-HAT were exposed to single doses of acoziborole from 20 to 1200 mg.

In study DNDiOXA001, single doses of acoziborole from 20 mg to 1200 mg were well tolerated overall in healthy subjects of sub-Saharan African origins. The most frequently reported adverse events (AEs) after acoziborole administration were gastrointestinal disorders, abnormalities on investigations (CPK increases, transaminase increases and thyroid hormone fluctuations) and central nervous system-related disorders (mainly headache). The frequency and severity were similar for subjects receiving active and placebo in this study. In addition, some of the abnormalities could be explained by the long follow-up period, which increased the probability of detecting non-drug-related fluctuations and use of activated charcoal. One serious adverse event (SAE) judged possibly related to acoziborole and therefore, a serious adverse reaction (SAR) of transient, mild "*asymptomatic hyperthyroidism*" (preferred term [PT]: hyperthyroidism; assessed as related to acoziborole), was reported after administration of a single dose of acoziborole 240 mg, on the basis of variations of thyroid function tests. It resolved spontaneously within 24 days of onset. This event triggered additional monitoring of thyroid function in subsequent cohorts and studies, however no thyroid-related safety signal has since been observed.

In study DNDi-OXA-02-HAT, 260 patients with HAT were included, among whom, 208 patients were exposed to a single dose of acoziborole 960 mg. A total of 27 treatment-emergent SAEs were reported in 21 patients exposed to acoziborole, all of which were assessed as not related to acoziborole. The most frequently reported SAEs were in the system organ class (SOC) Infections and infestations (n=10; 9 patients) or were related to neuropsychiatric disorders (n=9; 8 patients), including one fatal SAE in the SOC Nervous system disorders ("progressive peripheral ascending polyneuropathy"). Six cases of foetal exposure to acoziborole during pregnancies were reported. The outcomes were as follows:

- Pregnancies: all pregnancies had a normal duration with no complication;
- Deliveries:
  - 5 new-borns were in good general health at birth;

## 1.5. Choice of dose and dosing regimen

The dose of 960 mg has been confirmed as the therapeutic dose in the pivotal study DNDi-OXA-02-HAT. The single dose of the investigational product (IP) is recommended to be taken in the fasting state as a food effect study has not yet been performed.

## 1.6. Rationale for current study

Although the treatment options have advanced with the recent approval of fexinidazole (an effective 10-day oral treatment), there are still gaps with regards to the 2030 Public Health objective of sustained HAT elimination.

Indeed, the standard g-HAT case definition implies the demonstration of the parasite in any body fluid via microscopy. However, there are factors such as low parasitaemia and the complexity and low sensitivity of parasitological methods that make such demonstration difficult. It is known that there are some "indirect" signs of g-HAT that could indicate the presence of the parasites. The most known indirect signs of g-HAT are biological (positive antibody response to either available serological card agglutination test for trypanosomiasis [CATT], rapid diagnostic tests [RDTs; 11], or molecular tests) and clinical. In some circumstances, it has been suggested (11) to consider individuals presenting "indirect" signs, but without confirmatory observation of parasites in biological fluids (considered as g-HAT "suspected" individuals), as cases "eligible" for treatment. Only under special conditions, "suspected" g-HAT patients have been treated (12, 13, 14) since the complexity and toxicity of previously available treatment options typically precluded systematic treatment of these "suspects" due to an individual negative risk-benefit ratio. However, it has been demonstrated that a variable proportion (mainly depending on the prevalence) of such "suspects" are confirmed cases and, therefore, remaining as potential reservoirs of the parasite and a source of new infections hindering the efforts to eliminate the disease (11).

Acoziborole, as an oral single-dose treatment envisioned for all stages of g-HAT, is expected to help boost elimination efforts.

Acoziborole has been studied in an open-label pivotal Phase II/III trial (DNDi-OXA-02-HAT) in the DRC and Guinea. Eighteen months follow-up visits (primary endpoint) were successfully completed in August 2020 and study results (Tables, Figures and Listings) were issued in April 2021.

Given the encouraging safety and efficacy signs observed during the pivotal study conducted with acoziborole, DNDi opened a debate on 24 January 2019 in the frame of the ninth meeting of the sub-group "Integration of new tools into national and global policies" of the WHO g-HAT elimination network in order to define the hypothetical "preventive" use of acoziborole in the population of "suspected" g-HAT individuals. The meeting concluded that for such expanded use, there was a need to plan an additional trial to expand the safety data to complement the safety profile expected to be obtained in the pivotal trial. This would allow a better understanding of the risk-benefit of treatment with acoziborole in the population of g-HAT suspected but parasitologically unconfirmed individuals.

In the context of g-HAT elimination, the WHO HAT elimination Technical Advisory Group convened on 29 November 2019 and agreed (in the event of an effective and safe drug becoming available) to use bolder strategies coupled with case management to detect and treat any human reservoir to interrupt transmission.

A target product profile for a drug to be used in the different epidemiological scenarios was released (see Appendix 1).

The present clinical trial intends to provide responses to challenges encountered by National Sleeping Sickness Control Programmes (NSSCPs) of countries with regard to follow-up of unconfirmed g-HAT individuals (i.e. serologically positive and parasitology negative). Presently, the national policy of both DRC and Guinea is to advise this population to present regularly to health facilities for parasitological examinations until there is laboratory confirmation of parasite presence (thereby leading to treatment), or until seropositivity reverts to being negative (i.e. false seropositivity is concluded). Such an approach, dictated by the complexity of current treatment options, brings a lot of challenges and difficulties in terms of individuals' follow-up and implies that a certain number of infected (but unconfirmed) people remain as reservoirs; perpetuating disease transmission, and thereby hindering the global and national goal of eliminating HAT.

The availability of acoziborole and its unique characteristic of single oral dosing opens the door to put in place strategies to manage serologically positive but parasitologically unconfirmed populations, as long as an acceptable benefit-risk balance in the management of the referred population can be demonstrated.

In addition to this study, a sub-study named 'TrypSkin' is planned to assess the presence of extravascular dermal *T.b. gambiense* in the population enrolled. In an observational cohort study conducted in Guinea, the presence of extravascular dermal trypanosomes has been observed in individuals presenting with CATT positive results in plasma dilution  $\geq$ 1:4 but not confirmed by parasitological examination of blood and lymph (15). If these dermal trypanosomes correspond to *T.b. gambiense* subspecies and are able to infect vectors, these individuals could act as reservoirs for the transmission of g-HAT, hampering the elimination goal.

Therefore, in a larger scale and in multiple transmission foci, the TrypSkin sub-study aims to determine the presence/absence of *T.b. gambiense* in skin biopsies of subjects who will be willing to participate in the TrypSkin sub-study (optional participation) at enrolment, and at the end of the study. This will allow:

- Estimation of the prevalence of extravascular dermal *T.b. gambiense* in seropositive parasitologically unconfirmed individuals
- To compare different existing and novel methods of detection in blood and/or dermal *Trypanosoma brucei sensu lato* (*T. brucei s.l.*) and *T.b. gambiense*.

An exploratory efficacy evaluation will be performed with the tests included in the TrypSkin sub-study if the prevalence of extravascular *T.b. gambiense* in the skin at inclusion is superior to 2%, and the tests involved in the study demonstrate reliable and robust results to identify presence/absence of extravascular *T.b. gambiense* in the skin.

## 2. Study objectives and endpoints

## 2.1. Objectives

## 2.1.1. Primary objective

To assess the safety and tolerability of a single dose of acoziborole compared with placebo during a follow-up period of 4 months in seropositive individuals who are not confirmed parasitologically.

## 2.1.2. Secondary objectives

- To assess safety of acoziborole versus placebo in:
  - Haemato-biochemistry
  - Electrocardiogram (ECG) data at Day 5 (double delta versus baseline and time, age and sex matched comparison)
- To assess blood PK at Day 5 and Month 1

• To assess correlation between  $\Delta QTc$  measurements and acoziborole concentrations in blood at Day 5

## 2.1.3. Exploratory objectives (TrypSkin sub-study)

- To estimate the prevalence of extravascular dermal *T.b. gambiense* in seropositive individuals non-confirmed parasitologically (16).
- To compare the properties (sensitivity, specificity, accuracy, positive predictive value, negative predictive value, and repeatability) of different methods of detection of *T. brucei s.l.* and *T.b. gambiense* (polymerase chain reactions [PCRs], quantitative PCRs [qPCRs], multiplex Quantitative Reverse Transcriptase [qRT]-PCRs, Specific Highsensitivity Enzymatic Reporter unlocking [SHERLOCK], immuno-histochemistry [IHC]) in skin biopsies and blood samples.
- To determine the presence/absence of extravascular *T.b. gambiense* in skin biopsies of all subjects at enrolment, and at the end of the study.
- To assess the effectiveness of acoziborole on elimination of extravascular *T.b. gambiense* parasites in dermis with the methods or combination of methods, contingent on having better validity than *Trypanosoma brucei gambiense*-specific glycoprotein PCR (TgSGP-PCR) and provided that the prevalence of dermal trypanosomes by any method at baseline is greater than 2%.

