## 8.4. Exploratory assessments

For subjects participating in the TrypSkin exploratory sub-study, the following samples will be taken at screening (baseline) and 4 months (EoS):

- 3 mL fresh blood (in nucleic acid-preservative buffer) and 5 DBS
- Two 2 mm-skin-punch biopsies on the right back shoulder under local anaesthesia

Samples will be shipped to specialised partner laboratories (Institut National de Recherche Biomédicale [INRB], Institut Pasteur Guinea and Institut Pasteur Paris and Institute of Tropical Medicine [ITM] Antwerp) for the following analyses:

1- Molecular detection of trypanosomes:

- Common automatised extraction of total nucleic acids (TNAs) from fresh blood, DBS and skin biopsies
- On TNAs from fresh blood and skin (main validated diagnostic methods):
  - For all samples: TBR-PCR and 18S-PCR (*T. brucei s.l.*)
  - For TBR-PCR+ and/or 18S-PCR+ samples: T.b. gambiense-specific TgSGP-PCR
- On TNAs from fresh blood, DBS and skin (additional methods to be tested):
  - o qPCR detection using at least 2 targets
  - Multiplex RT-qPCR detection using novel targets
  - CRISPR-derived approach (SHERLOCK)
- 2- Immuno-histochemical detection of dermal trypanosomes:
  - At least 2 automatised IHC on Formalin-Fixed Paraffin-Embedded (FFPE) skin sections for all subjects with *T. brucei*-specific staining (Anti-Invariable Surface Glycoprotein 65 [ISG65] and Anti-cross reacting determinant [CRD] and secondary polymer amplification
  - Automatised acquisition and double *in silico* blind reading, pictures annotation and archiving
- 3- Preliminary tests for the detection of trypanosomes by Raman spectroscopy:
  - For each subject at each time point, one DBS from the field and one FFPE slide generated for IHC at IP Paris will be scanned by Raman spectroscopy at the University of Glasgow in the context of an exploratory procedure based on the measurements of biophysical parameters associated to the presence of trypanosomes.

• The results will not be uploaded in the central data base as the final analyses will rely on machine learning approaches after the end of the study.

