#### Primary diagnostic parameter

A subject is considered positive to extravascular dermal *T.b. gambiense* if TgSGP-PCR test in skin is positive.

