#### Primary statistical test

A Cochran-Mantel-Haenszel test using sites as strata will compare acoziborole and placebo occurrence rate at 4 months of positive dermal. The overall OR will be estimated for each parameter as well as the ERs and NTT.

In case of small proportions, the exact Cochran-Mantel-Haenszel test will be performed.

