#### Analysis of secondary clinical and diagnostic parameters

Dermal trypanosomes may be the cause of dermatitis and/or pruritus, therefore a secondary clinical and exploratory question of interest is:

Does acoziborole reduce the occurrence at 4 months of dermatitis and/or pruritus signs or symptoms in comparison with placebo?

The secondary clinical parameter will be the occurrence/presence of dermatitis and/or pruritus signs or symptoms at 4 months.

The same approach as for the primary diagnostic parameter will be used for the occurrence of dermatitis or pruritus.

Current specific molecular diagnostic methods are known to be of low sensitivity. The TrypSkin sub-study aims at testing new methods to overcome this weakness.

Secondary diagnostic parameters will be the occurrence of IHC+ results in skin, TBR-PCR+ and/or 18S-PCR+ in blood and/or skin, as well as novel diagnostic parameters corresponding to occurrence of positive results by qPCRs, multiplex RT-qPCRs and SHERLOCK in blood and/or skin.

The secondary analyses will be exactly the same as the primary diagnostic parameters.

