#### 10.9. Interim analysis

For the TrypSkin sub-study, an interim analysis for futility will be performed once the baseline data of 50% of subjects will be collected. If the occurrence rate of positivity by any diagnostic method in any sample at baseline lead to less than 2%, then the recruitment in the TrypSkin sub-study will be stopped.

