5.3. Exploratory Objectives (Sub-study) Analysis

5.3.1. Exploratory Analysis

The primary set of subjects for exploratory efficacy analyses is the Safety set composed of subjects who participated in the TrypSkin sub-study. The primary exploratory objective is to establish whether acoziborole reduces the occurrence at 4 months of dermal trypanosomes in comparison with placebo. The exploratory efficacy will be evaluated using diagnostic and clinical endpoints. The primary diagnostic endpoint will be dermal trypanosome positive if TgSGP-PCR in skin is positive and the clinical endpoint will be the occurrence/presence of dermatitis and/or pruritus symptoms at 4 months. The occurrence rate of positive dermal trypanosome at 4 months based on the primary diagnostic parameters will be the primary measure of interest because the sample size is under control, and it corresponds to a measure of the level of potential transmission of reservoirs. The magnitude of the treatment effect will be the odds ratio of positive dermal trypanosomes. A Cochran Mantel Haenszel test using sites as strata will be used to compare acoziborole and placebo occurrence rate at 4 months of positive dermal trypanosome as well as occurrence of dermatitis and/or pruritus symptoms. In case of small proportions, the exact Cochran-Mantel-Haenszel (CMH) test will be performed. The Breslow-Day test of homogeneity of the odds ratio across sites will be performed to assess the generalizability of the treatment effect. If the test is significant, a forest plot will be provided to display the heterogeneity of the magnitude of treatment effect across sites and to detect sites explaining the heterogeneity.

As the odds ratio is not easy to interpret when the rate of positive subjects in the placebo group is not small ($P_0 > 0.05$), the odds ratio (OR) will be converted into the risk ratio (RR) using the following formula:

$$RR = \frac{P_1}{P_0} = \frac{OR}{(1 - P_0) + P_0 \times OR)}$$

where P_1 and P_0 are the estimated proportions of positive subjects in the acoziborole group and placebo group respectively. The excess rate $(P_1 - P_0)$ will also be estimated as a secondary measure of the magnitude of the treatment as well as the NTT (number of subjects needed to treat to get one less positive subject at 4 months in acoziborole group. The exploratory efficacy analysis results will be presented and individual data listing.

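### Do the differing 2% conditions leave it unclear whether the TrypSkin efficacy comparison is run?

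*Protocol*

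**What the plan says.** Four sets of statements bear on the point.

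- **Protocol 1.6 (rationale).** An exploratory efficacy evaluation, using the tests included in the sub-study, is made if *T.b. gambiense* "in the skin at inclusion is superior to 2%, and the tests involved in the study demonstrate reliable and robust results".
- **Protocol 2.1.3 and SAP 1.1.1.3 (objectives).** Effectiveness on dermal parasites is assessed with methods, or combinations of them, that prove more valid than TgSGP-PCR, "provided that the prevalence of dermal trypanosomes by any method at baseline is greater than 2" per cent.
- **Protocol 10.8 and SAP 5.3.1 (analysis).** A subject counts as positive for dermal *T.b. gambiense* "if TgSGP-PCR test in skin is positive". The protocol states the test as "A Cochran-Mantel-Haenszel test using sites as strata will compare acoziborole and placebo occurrence rate at 4 months of positive dermal", and SAP 5.3.1 says the same: "A Cochran Mantel Haenszel test using sites as strata will be used to compare acoziborole and placebo occurrence rate at 4 months". Neither section mentions a 2% threshold.
- **Protocol 10.9 and SAP 2.5 (interim look at half the baseline data).** "If the occurrence rate of positivity by any diagnostic method in any sample at baseline lead to less than 2" per cent, sub-study recruitment stops. SAP 2.5 adds the reason: the effect on dermal parasites could not then be assessed.

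Two facts about the tests matter. Protocol 8.4 runs the species-specific test only on screened positives ("For TBR-PCR+ and/or 18S-PCR+ samples: T.b. gambiense-specific TgSGP-PCR"), and 10.8 concedes that "Current specific molecular diagnostic methods are known to be of low sensitivity".

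**The concern.** Read side by side, the sections seem to give different answers to one question: is the Month 4 comparison made? One asks for *gambiense* in skin, one for any dermal trypanosome by any method, and one asks for nothing.

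The counts are nested. If *T.b. gambiense* positivity means TgSGP-PCR positive, it can only arise among TBR-PCR or 18S-PCR positives, so its rate cannot exceed the any-method skin rate. The low sensitivity of the specific test makes a gap between the two likely. 'Any method' could also mean each test taken singly or the union of them all.

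The interim rule counts blood and dried blood spots as well as skin, although its stated reason concerns skin alone. Recruitment could therefore continue with skin positivity under 2%.

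At stake would be a decision to report, or not report, a treatment comparison under a condition that could be interpreted after the results were known.

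**Working it through.** **1. The plan's own figures.** The 690 evaluable subjects come from z²p(1−p)/d² with p = 0.20 and d = 0.03: 1.96² × 0.16 / 0.0009 = 683, close to the tabulated 690. Then 690 × 1.05 = 724.5, giving 725. Power for 175 placebo against 525 acoziborole, 20% against 1%, two-sided 5%, is above 99.99%, as stated. The 2% threshold is not derived in either document.

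**2. When can 1.6 and 2.1.3 disagree?** Take 1.6 as a TgSGP-PCR count (an assumption; 1.6 names no test). Since 2% of 690 is 13.8, the condition is met at 14 or more positives. Let A ~ Bin(690, q) be the any-method skin positives and T | A ~ Bin(A, f) those confirmed by TgSGP-PCR. The table gives P(A ≥ 14 and T ≤ 13), with q and f assumed.

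| q | f = 0.9 | f = 0.7 | f = 0.5 | f = 0.3 |
|---|---|---|---|---|
| 3% | 6% | 37% | 79% | 95% |
| 4% | <1% | 8% | 48% | 96% |
| 5% | 0% | 1% | 18% | 84% |
| 10% | 0% | 0% | 0% | 5% |
| 20-25% | 0% | 0% | 0% | 0% |

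If 1.6 counts positivity by any of the sub-study's tests (f = 1), the disagreement is 0% throughout.

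**3. Does 2.1.3 conflict with 10.8 and SAP 5.3.1?** The 2.1.3 condition is attached to methods of better validity than TgSGP-PCR. TgSGP-PCR cannot be better than itself, so the clause cannot sensibly govern the TgSGP-PCR comparison. That comparison is a separately listed primary exploratory endpoint (protocol 2.2.3, SAP 1.1.1.6). The clause fits the last step of 10.8 and SAP 5.3.6, where tests are ranked and the primary analysis is redone on the best one. That ranking uses placebo-group agreement between baseline and Month 4, so it belongs to the final analysis. On this reading, TgSGP-PCR is analysed unconditionally and better methods are analysed above 2%.

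**4. Is an unconditional comparison sound?** Both analysis sections provide an exact Cochran-Mantel-Haenszel test for small proportions, and SAP 3.1 requires 95% intervals on all estimates. With a 95% effect and 175 against 525 subjects, power by two-sided Fisher test is 22% at 1% skin positivity and 59% at 2%. Low prevalence thus costs precision, not validity. A null result there should not be read against the 99.99%, which belongs to 20%.

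**5. The interim rule.** Half of 725 is about 362, and 2% of 362 is 7.24, so recruitment stops at 7 or fewer positives. P(Bin(362, r) ≤ 7) is 97% at r = 1%, 32% at 2.5%, 15% at 3% and 2% at 4%. If skin positivity were 1% and any-sample positivity 3%, a skin-based rule would stop with probability 97% and the written rule with 15%. The logic still runs the right way: the any-sample count is the largest, so a rate below 2% there implies skin below 2%, and SAP 2.5's reason supports stopping. Neither document says that passing the rule shows dermal efficacy to be assessable.

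**6. Each test or the union.** Protocol 8.4 gives 14 method-by-sample results: TBR-PCR and 18S-PCR in blood and skin (4), three novel methods in blood, dried blood spots and skin (9), and IHC in skin (1). Six are in skin. With no true positives and independent errors, the union rate is 1 − s¹⁴ in any sample and 1 − s⁶ in skin. At assumed specificities of 99.9%, 99.8% and 99.5% this is 1.4%, 2.8% and 6.8% in any sample, and 0.6%, 1.2% and 3.0% in skin. Positively correlated errors, plausible given the common nucleic-acid extraction, pull these toward a single test's 0.1%, 0.2% and 0.5%.

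**The case for a change.** The strongest case for a change is that 1.6 states an operative condition, not mere background. A reader who carries a threshold from the front of the protocol into 10.8 must still choose between 1.6 and 2.1.3. The sponsor's own 2% threshold shows that low prevalence was contemplated, and that is exactly where the versions part. Harmonising the wording would cost only text.

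Part of this stands. The wordings differ, 'any method' is undefined, and neither analysis section says whether the threshold reaches the TgSGP-PCR comparison. One sentence in the SAP would have been tidier.

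It does not carry the conclusion, for three reasons. First, the larger disagreement figures rest on a TgSGP-PCR-only reading that 1.6 does not state. The documents also use dermal trypanosome and dermal *T.b. gambiense* loosely: SAP 5.3.1 defines the former by TgSGP-PCR.

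Second, the risk of choosing after the fact is limited. The threshold depends on baseline data, blinding holds until database lock (protocol 7.7.1), departures must be justified in the study report (10.11), and analyses outside the SAP are labelled post hoc (SAP section 1). The default is to report what SAP 5.3.1 specifies.

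Third, a rewrite would have to settle species, tests, and single test or union, and each choice has a cost. A TgSGP-PCR-only condition may withhold the comparison because that test is insensitive; a union condition may open it on false positives. A lenient any-sample interim rule also protects the prevalence and diagnostic objectives, the latter of which use blood and dried blood spots.

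**Conclusion.** No change is needed. This is loose wording in an exploratory sub-study that analysts can resolve sensibly: run the TgSGP-PCR comparison as SAP 5.3.1 specifies, and apply the 2% condition to the re-analysis on a better-ranked method. The interim rule is lenient but consistent with its reason for stopping.

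The practical effect is confined to low baseline prevalence. The chance that 1.6 and 2.1.3 diverge is appreciable below roughly 5-10%, ranging at a 3% any-method rate from 6% to 95% as TgSGP-PCR confirmation falls from 90% to 30%. It is 0% at the hypothesised 20-25%. These figures rest on assumed prevalence and confirmation rates and on reading 1.6 as a TgSGP-PCR count; if 1.6 means any sub-study test, they vanish. The sample size, the primary test and the main safety objective are unaffected.
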